7.0 Sharing of Results with Participants

7.1 Sharing results:

Given the pragmatic nature of this study, participants will receive laboratory test results, which will be shared by a study team member. However, for the genetic analysis (DNA collection and genotyping), only aggregate results will be shared with participants as described below.

7.2 Sharing of genetic testing:

7.2.1 Disclosure of results:

Only aggregate results of the genetic analyses (DNA collection and genotyping) will be shared with participants. We are not planning to disclose individual results of genetic testing to participants.

7.2.2 If returning results to participants:

MEDICAL PROTOCOL (HRP-590)

PROTOCOL TITLE: Pharmacokinetics and Pharmacodynamics of Topiramate for Weight Loss in Youth: PHARMATOP

VERSION DATE: 05/03/2024

- *Aggregate or individual results:* Aggregate.
- *Laboratory results:* N/A
- *Plan for return of results to participants:* Results will be returned via a study website after publication of the study results.
- *Types of results to be returned to participants:* Participants will not be provided with complete datasets. We will return lay summaries of the publications to the participants.

7.2.3 Future analysis of genotypes: N/A

8.0 Study Population

8.1 Inclusion Criteria:

- Body Mass Index (BMI) \geq 1.2 times the 95th percentile (age and sex-adjusted) and/or BMI \geq 35 kg/m²
- Ages 12 to <18 years old
- If recruited from PWMC: Deemed appropriate candidates to receive topiramate (without contraindications) for weight loss by an obesity medicine specialist at the University of Minnesota

8.2 Exclusion Criteria:

- History of metabolic/bariatric surgery
- Obesity associated with a diagnosed genetic disorder (i.e. monogenic obesity, Prader-Willi, Bardet-Biedl syndrome)
- Clinically diagnosed hyperthyroidism or uncontrolled hypothyroidism as determined by local medical monitor ([name]) (who is a board certified endocrinologist)
- History of acute angle closure glaucoma. Individuals with other types of glaucoma will need approval from the participant's ophthalmologist to be enrolled.
- History of nephrolithiasis
- History of a seizure disorder (aside from febrile seizures)
- Major psychiatric disorder as determined by local medical monitor
- History of bulimia nervosa or anorexia nervosa
- History of suicide attempt within one year of the screening visit
- History of active suicidal ideation or self-harm within 30 days of the screening visit
- Current or recent (< 6 months prior to enrollment) use of topiramate or phentermine/topiramate
- Current or recent (< 6 months prior to enrollment) use of other anti-obesity medication(s) defined as metformin, orlistat, phentermine, liraglutide/semaglutide (or other GLP1-RAs), naltrexone, and/or combination naltrexone/bupropion (monotherapy use of bupropion is not an exclusion), **unless** participant has been on stable doses for \geq 6 months. Of note, if a dose of phentermine was increased from 15 mg daily to 18.75 mg daily during this period, it is not considered a dose increase.

MEDICAL PROTOCOL (HRP-590)

PROTOCOL TITLE: Pharmacokinetics and Pharmacodynamics of Topiramate for Weight Loss in Youth: PHARMATOP

VERSION DATE: 05/03/2024

- Current or recent (< 6 months prior to enrollment) use of medication(s) associated with weight gain (e.g. oral steroids, anti-psychotics), **unless** participant has been on stable doses of such medication(s) for \geq 6 months
- Current or recent (< 6 months prior to enrollment) use of long-acting stimulant medications, **unless** participant has been on stable doses of such medication for \geq 6 months. In terms of short-acting ADHD stimulant medications, the PI will determine eligibility based on weight and dose (no studies have shown this contributes to weight outcomes).
- Baseline bicarbonate $<$ 18 mmol/L
- Baseline creatinine $>$ 1.2 mg/dL
- Females: pregnant, planning to become pregnant, or, if sexually active, unwilling to use 2+ acceptable contraceptive methods during the study period

8.3 Screening:

Patients seen in the University of Minnesota PWMCs who are deemed appropriate candidates to receive topiramate (without contraindications) for weight loss by an obesity medicine specialist will be referred for this study.

Screening/Baseline Visit (Visit 1):

Participants will be asked to present at this visit after having fasted for \geq 12 hours. At this visit, the participant's parent/legal guardian will be taken through the consent process and will sign the parental consent form, and the participant will be asked to sign the assent form, after all have had the opportunity to learn about the study and ask any questions they may have. The participant will then undergo the following:

- Review of inclusion/exclusion criteria
- Demographics including age, sex, self-reported race/ethnicity, home address, total family combined income, parents' level of education and employment status
- Physical exam and tanner stage. The physical examination will not need to be repeated if performed by a CPOM faculty member, pediatric weight management provider, and/or pediatric endocrinologist within the last 30 days before Screening/Baseline visit. A trained professional can perform the Tanner staging.
- BMI/Anthropometrics: height, weight, waist and hip circumference, and BMI
- Blood pressure and heart rate
- Pregnancy test for females
- Contraceptive counseling
- Review of medications
- Blood draw for safety labs (creatinine and bicarbonate) and cardiometabolic risk labs (lipids, glucose, insulin, and A1c)
- Genotyping (via saliva collection)
- iDXA (body composition)
- Bioelectrical impedance analysis (via Tanita Scale)
- Eating behavior and physical activity questionnaires (hunger/satiety visual analog scales, AEBQ, FCQ-T-r, dYFAS, RED-5, BEVQ-15, PAQ-A)
- Safety questionnaire for eating disorders (EDE-Q)

MEDICAL PROTOCOL (HRP-590)

PROTOCOL TITLE: Pharmacokinetics and Pharmacodynamics of Topiramate for Weight Loss in Youth: PHARMATOP

VERSION DATE: 05/03/2024

- Depression and suicide screening (PHQ-9 and C-SSRS). Participants whose tests show that they have active suicidal ideation will be referred to their own mental health provider, have a mental health referral generated or be referred to the emergency department
- Neurocognitive testing (COWA test, NIH-TB List Sorting Working Memory Test, NIH-TB Pattern Comparison Processing Speed Test)
- Lifestyle and registered dietitian counseling

Week 2 (± 7 days from enrollment):

- Side effects, inter-current illnesses, medication review and adherence (via phone call)

Week 4 (± 7 days from enrollment):

- Side effects, inter-current illnesses, medication review and adherence (via phone call)

Week 6 (± 7 days from enrollment; Visit 2):

- BMI/Anthropometrics
- Blood pressure and heart rate
- Blood draw for safety labs (creatinine and bicarbonate)
- Pregnancy test for females
- Topiramate concentration
- Bioelectrical impedance analysis (via Tanita Scale)
- Eating behavior and physical activity questionnaires (hunger/satiety visual analog scales, AEBQ, FCQ-T-r, dYFAS, RED-5, BEVQ-15, PAQ-A)
- Safety questionnaire for eating disorders (EDE-Q)
- Depression and suicide screening (PHQ-9 and C-SSRS)
- Neurocognitive testing (COWA test, NIH-TB List Sorting Working Memory Test and NIH-TB Pattern Comparison Processing Speed Test)
- Lifestyle and registered dietitian counseling
- Side effects, inter-current illnesses, medication review
- Adherence (via electronic prescription bottle review and counting pills)

Week 8 (± 7 days from enrollment; Visit 3; lab draw only):

- Topiramate concentration
- Side effects, inter-current illnesses, medication review (via phone call or in-person)
- Adherence (via electronic prescription bottle review and counting pills)
- Suicide screening (C-SSRS)
- Drug dispensing

Week 10 (± 7 days from enrollment; Visit 4):

- BMI/Anthropometrics
- Blood pressure and heart rate

MEDICAL PROTOCOL (HRP-590)

PROTOCOL TITLE: Pharmacokinetics and Pharmacodynamics of Topiramate for Weight Loss in Youth: PHARMATOP

VERSION DATE: 05/03/2024

- Pregnancy test for females
- Topiramate concentration
- Bioelectrical impedance analysis (via Tanita Scale)
- Depression and suicide screening (PHQ-9 and C-SSRS)
- Neurocognitive testing (COWA test, NIH-TB List Sorting Working Memory Test, NIH-TB Pattern Comparison Processing Speed Test)
- Side effects, inter-current illnesses, medication review
- Adherence (via electronic prescription bottle review and counting pills)

Week 14 (± 7 days from enrollment; Visit 5):

- Physical exam, performed by a trained pediatrician
- BMI/Anthropometrics
- Blood pressure and heart rate
- Blood draw for cardiometabolic risk labs (lipids, glucose, insulin, and A1c)
- Pregnancy test for females and questionnaire about the testing
- Topiramate concentration
- Bioelectrical impedance analysis (via Tanita Scale)
- Safety questionnaire for eating disorders (EDE-Q)
- Eating behavior and physical activity questionnaires (hunger/satiety visual analog scales, AEBQ, FCQ-T-r, dYFAS, RED-5, BEVQ-15, PAQ-A)
- Neurocognitive testing (COWA test, NIH-TB List Sorting Working Memory Test, NIH-TB Pattern Comparison Processing Test)
- Side effects, inter-current illnesses, medication review
- Suicide screening (C-SSRS)
- Adherence (via electronic prescription bottle review and counting pills)

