• NIH-TB List Sorting Working Memory Test					
• NIH-TB Pattern Comparison Test					
Lifestyle Counseling	x	x			
Registered Dietician Visit	x	x			
Drug Dispensing	x		x		
Adherence	← Assessed at in person visits via electronic prescription bottles and pill count and at weeks 2 and 4 via phone call →				
Side Effects, Inter-current Illnesses, Concomitant Medications Review	← Assessed weeks 6, 8, 10, and 14 at study visit; weeks 2, and 4 via phone call →				

¹ Will be reviewed by study principal investigator and/or co-investigator

² Demographics including age, sex, race/ethnicity

³ Physical exam does not need to be repeated if one was done by CPOM faculty, in the pediatric weight management clinic, or by a pediatric endocrinologist within 30 days prior to Screening/Baseline visit. Tanner determined by Marshall-Tanner criteria examining breast and pubic hair development (girls) or genitalia and pubic hair (boys); to be performed by a trained professional.

⁴ Height, weight, BMI, waist circumference, hip circumference

⁵ Creatinine (to assess renal function) and bicarbonate (to assess for presence of metabolic acidosis)

⁶ Lipids (total, LDL-, HDL-cholesterol, triglycerides), glucose, insulin, hemoglobin A1c.

⁷ DNA collection via salivary collection kits

⁸ iDXA to include total and regional body fat measures

⁹ Performed using Tanita scale

¹⁰ Including hunger/satiety Visual Analog Scales, Adult Eating Behavior Questionnaire (AEBQ), Food Craving Questionnaire-Trait-Reduced (FCQ-T-r), Dimensional Yale Food Addiction Scale 2.0 for Children (dYFAS), Reward Based Eating Drive Scale X5 (RED-5), and Physical Activity Questionnaire for Adolescents (PAQ-A)

¹¹ Assessed via the Beverage Intake Questionnaire 15 (BEVQ-15)

¹² PHQ-9 to be conducted at Baseline/Screening, Week 6 and Week 10. Columbia-Suicide Severity Rating Scale (C-SSRS) to be conducted at all visits

¹³ Controlled Oral Word Association (COWA) test, NIH-TB List Sorting Working Memory Test and NIH-TB Pattern Comparison Test

¹⁴ Urine pregnancy preferred, but serum may be utilized. Females who undergo pregnancy testing will be asked to complete a questionnaire about their experience at the Week 14 visit

MEDICAL PROTOCOL (HRP-590)

PROTOCOL TITLE: Pharmacokinetics and Pharmacodynamics of Topiramate for Weight Loss in Youth: PHARMATOP

VERSION DATE: 05/03/2024

5.2 Study Procedures:

Anthropometric Measurements and Body Fat Composition:

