15.0 Statistical Considerations

15.1 Data Analysis Plan:

PopPK analysis will be conducted using NONMEN® following best practice guidelines set forth by Byon et al.⁵⁶ We will assume that the structural model of topiramate follows a one-compartment model with 1st-order absorption and elimination per previous topiramate studies.²³⁻²⁵ Topiramate concentrations (collected 4, 6, 8, and 12 weeks after 75 mg or maximum-tolerated topiramate dose reached) will be modeled using non-linear mixed effects (NLME). Topiramate exposure (assessed by area under the curve (AUC)), as well as additional variables including apparent clearance, volume of distribution, and inter-individual variability will be estimated with popPK, described in **Section 15.3**. The effects association of topiramate exposure (AUC) on weight loss outcomes (BMI reduction, changes in eating behaviors and cardiometabolic risk labs) will be performed using linear regression with robust estimation for confidence intervals and p-values. We will also explore potential non-linear relationships with cubic splines.

15.2 Power Analysis:

In line with the goals of this pilot study, our sample size was chosen to strike a balance between recruitment, feasibility, potential attrition, and the amount of data deemed necessary to inform the aims and design of a subsequent NIH R01. Results from previous simulations and statistical methods for repeated measures outcomes using sparse sampling in popPK suggest that bias and precision are acceptable as sample sizes approach 50.⁵⁷⁻⁵⁹ Assuming 25% drop-out, higher than usual for CPOM clinical trials (10-15%), we will recruit 65 participants. The power will depend on the range of values observed for the exposure predictor (AUC). Based on the variability observed from a pilot study of similar dose and age, and allowing for drop-out of as many as 15, we will have 80% power for an association of 4.75kg per 20 mcg*h/ml.⁶⁰

15.3 Statistical Analysis:

Pharmacokinetic Modeling (dose-exposure relationships):

Topiramate concentrations will be modeled using a non-linear mixed effects (NLME) regression

MEDICAL PROTOCOL (HRP-590)

PROTOCOL TITLE: Pharmacokinetics and Pharmacodynamics of Topiramate for Weight Loss in Youth: PHARMATOP

VERSION DATE: 05/03/2024

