implemented in NONMEM® (ICON Development Solutions, [name]). NLME is robust with respect to sparse data sets such as ours, hence appropriate for this analysis. Compartment models best describing topiramate will be selected based on diagnostic plots and fall in objective function values (OFVs). Covariates known to effect drug disposition (e.g. BMI, sex, race/ethnicity, genomics, as determined by a genetic risk score (GRS) will be included in the model-building algorithms. An automated stepwise covariate model (SCM) procedure will be used to screen covariates.³¹ The SCM involves forward selection and backward elimination steps: forward addition followed by backward deletion. Covariates that upon inclusion reduced the OFV by at least 3.84 (statistical significance of $p<0.05$, based on a Chi-squared distribution (degrees of freedom (df) = 1)), will be sequentially added. After stepwise addition of all significant covariates, backward deletion will be performed wherein removal of covariates that increase the OFV by at least 6.84 (statistical significance of $p<0.01$ based on a Chi-squared distribution (df = 1)), will be considered significant. Final model parameter estimates and their 95% confidence intervals will be qualified by re-estimation using a nonparametric bootstrap approach generating 1,000 bootstrap datasets. Parameter estimates are rank ordered and the values at the 2.5% and 97.5% of the rank order are used as the lower and upper bounds of the bootstrap 95% confidence interval. The 50th percentile (median) is used as the bootstrap parameter estimate.³¹

Pharmacodynamic Modeling (exposure-response relationships):

The association of topiramate exposure (AUC) on weight loss outcomes (BMI reduction, changes in eating behaviors and cardiometabolic risk labs) will be performed using linear regression, adjusting for model covariates, with robust estimation for confidence intervals and p-values. We will also explore potential non-linear relationships utilizing cubic splines.

15.4 Data Integrity:

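### Current anti-obesity co-medication is allowed at entry and recorded, but the primary PD regression does not name it as a covariate

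*Combined protocol and SAP*

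**What the plan says.** **Eligibility (section 8.2).** Metformin, orlistat, phentermine, GLP-1 agonists, naltrexone and naltrexone/bupropion are grounds for exclusion if current or recent, unless the "participant has been on stable doses for" 6 months or longer. Two further provisions widen the group: "monotherapy use of bupropion is not an exclusion", and "if a dose of phentermine was increased from 15 mg daily to 18.75 mg daily during this period, it is not considered a dose increase". Participants with "use of medication(s) associated with weight gain (e.g. oral steroids, anti-psychotics") can also enter on stable doses, as can users of long-acting stimulants.

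**Data collected.** Medications are reviewed at the baseline visit (section 8.3). Table 1 schedules "Side Effects, Inter-current Illnesses, Concomitant Medications Review" for the phone calls at weeks 2 and 4 and for every visit from week 6.

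**Analysis.** The primary PD outcome is percent change in BMI from baseline (section 3.1). Section 15.1 says the exposure-response analysis "will be performed using linear regression with robust estimation for confidence intervals and p-values" and names no covariates. Section 15.3 says it "will be performed using linear regression, adjusting for model covariates" and does not say which these are. The only covariates listed in section 15 appear under the PK model: BMI, sex, race/ethnicity and a genetic risk score, given as examples of factors that affect drug disposition. No adjustment, subgroup or sensitivity analysis mentions co-medication.

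**The concern.** AUC is observed, not assigned. Everyone is titrated towards the same daily dose, so differences in AUC come from disposition, tolerability and adherence. In such a regression, covariates should be chosen for their bearing on the outcome, and on the outcome together with exposure. A list built by screening for effects on drug disposition is not designed for that.

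Section 8.2 shows that the plan regards these drugs as weight-active, since it restricts their use for that reason. Two things are at stake:

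- **Precision.** Any remaining effect of the other drug on BMI change stays in the error term.
- **Bias.** If users also differ from non-users in AUC, part of that effect is attributed to topiramate exposure.

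The two are separate. The first needs only an effect on the outcome; the second also needs an association with AUC.

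**Working it through.** **1. The plan's own figures.** Section 15.2 recruits 65 and allows for 15 lost: 65 - 15 = 50 evaluable. Working back from 50 with 25% drop-out gives 50/0.75 = 66.7, or 67, close to the planned 65. The stated 80% power is for 4.75 kg per 20 mcg\*h/ml. It cannot be reproduced, because the SD of AUC, the residual SD and the significance level are not given. It is also in kg, whereas the primary PD outcome is percent BMI change. I therefore take 80% as the starting point and ask what it implies.

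Let λ be the slope per SD of AUC divided by the residual SD. With n = 50, two-sided 5% (assumed), 48 df and noncentrality λ√50, 80% power requires λ = 0.4044.

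**2. On the BMI scale.** The only SD given for BMI response is 5.8% (section 2.2: 28 youth, retrospective, 6 months). Taking it as the residual SD without co-medication in the model, the detectable slope is 0.4044 × 5.8 = 2.35 percentage points per SD of AUC.

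**3. Precision.** Let p be the proportion of users and d their remaining difference in BMI change, in percentage points. The documents give neither. Variance left in the error is p(1-p)d², as a share of 5.8² = 33.64. After adjustment the SD is √(33.64 - p(1-p)d²), λ rises in proportion, and the test has 47 df.

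Example, p = 0.2 and d = 2: 0.16 × 4 = 0.64; 0.64/33.64 = 1.9%; SD = √33.00 = 5.74; power 80.7%.

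| Users p | Difference d | Share of variance | Power after adjustment (from 80.0%) |
|---|---|---|---|
| 0.1 | 1 | 0.3% | 80.1% |
| 0.2 | 1 | 0.5% | 80.2% |
| 0.1 | 2 | 1.1% | 80.4% |
| 0.2 | 2 | 1.9% | 80.7% |
| 0.4 | 2 | 2.9% | 81.1% |
| 0.2 | 4 | 7.6% | 83.0% |
| 0.4 | 4 | 11.4% | 84.5% |

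**4. Bias, only if users differ in AUC.** Let g be the gap in mean AUC between users and non-users, in SDs of AUC. The bias per SD of AUC is d × p(1-p) × g.

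| p, d, g | Bias (points per SD of AUC) | Share of 2.35 | False-positive rate |
|---|---|---|---|
| any, any, 0 | 0 | 0% | 5.0% |
| 0.2, 2, 0.2 | 2 × 0.16 × 0.2 = 0.064 | 2.7% | 5.1% |
| 0.2, 2, 0.5 | 2 × 0.16 × 0.5 = 0.16 | 6.8% | 5.4% |
| 0.4, 4, 0.5 | 4 × 0.24 × 0.5 = 0.48 | 20.5% | 8.8% |

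**5. Power of an analysis without users.** With the same λ = 0.4044, noncentrality λ√n and n - 2 df, n = 50(1-p) gives 76% at n = 45 (10% users), 70% at n = 40 (20%) and 57% at n = 30 (40%).

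**The case against.** **The adjustment set is undefined rather than restricted.** A reader might infer that the PD model adjusts only for covariates kept in the PK model. Section 15.3 does not say so. Its phrase is undefined, the PK list is introduced as examples, and section 2.1 mentions other baseline characteristics. This stands: the documents show that co-medication is not named, not that it is ruled out.

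**The stability rule is a real safeguard.** The outcome is change from baseline, so much of the effect of a drug taken stably for 6 months is already in baseline BMI. Only its further effect over 14 weeks matters. A remaining difference of 2-4 points would be 2/4.9 = 41% to 4/4.9 = 82% of the whole mean 6-month BMI reduction in section 2.2, so the upper end is generous. This stands, and is why the d = 1 rows belong in the table. The safeguard is partial: it looks back from enrolment, and I found no analysis rule for changes in co-medication during the study.

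**Confounding is not shown.** A reader might infer that the slope is biased. All participants share a target dose, and section 4.1 reports dose reduction in one of 30 in the previous trial. BMI, one possible link, is among the listed PK covariates, and a drug that altered topiramate clearance could enter through covariate screening. Nor is chance imbalance bias: it averages to zero and is covered by the confidence interval. All this stands.

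**One pooled indicator would be crude.** Weight-gain drugs and stimulants may act in opposite directions, so putting them in one variable could cancel their effects. This also stands and shapes the fix.

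What remains is that a specific, recorded, weight-active baseline variable is missing from the named analyses of a non-randomised exposure.

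**Conclusion.** The point holds as a minor improvement to the analysis. Participants on other anti-obesity drugs can enrol, their use is recorded, and no PD analysis names it.

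Over 10-40% users and a remaining difference of 2-4 points, adjustment raises power from 80% to about 80.4-84.5%. With 1-2 points in 10-20% of participants the gain is under one percentage point. These figures assume n = 50, two-sided 5%, an SD of 5.8% carried over from 6 months, and the plan's 80% transferred from kg to percent BMI change. Prevalence and effect are assumptions.

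The documents do not support the stronger conclusion that the exposure-response slope is confounded. That needs users and non-users to differ systematically in AUC. If they did, the bias in the cases shown would be 2.7-20.5% of the detectable slope; if not, it is zero. Adjustment is inexpensive protection against a possibility, not the correction of a demonstrated error.

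**What to change.** 1. In sections 15.1 and 15.3, use one description of the primary PD regression and list its covariates in advance. Include a yes/no indicator for current anti-obesity co-medication at baseline, defined from the drug list in section 8.2, and state whether bupropion alone counts.
2. Add a sensitivity analysis of the primary PD outcome without users, reported as lower-powered (section 8.2 sets no cap, so the loss is not known in advance). Judge it by whether the slope estimate is similar, not by its p-value.
3. Do not combine weight-gain drugs and stimulants in one indicator. Handle each separately, or only in sensitivity analyses if few participants take them.

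The cost is one degree of freedom in the primary model and some wording in section 15. No new data are needed, and eligibility is unchanged.
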